Anesthetic and surgical technique will be identical for both groups, and will only differ in type of instrumentation used. Patients are normally given an spinal anaesthetic for intra-operative anesthesia. Patients are placed supine with a 5L saline bag beneath the buttock on the operated side and a tourniquet around the thigh. After appropriate prepping and draping, the tourniquet is inflated and a midline skin incision is used, followed by a medial para-patellar arthrotomy. This allows access to the joint for bone cuts using the appropriate instrumentation, soft tissue balancing, and component implantation. To reduce the incidence of infection, all patients are given 1 pre-op and 3 post-op doses of cephazolin or vancomycin (if penicillin allergic), and body exhaust suits are used by all surgical staff in the operating room. As per our group's normal routine, AP and lateral x-rays of the knee are performed in the recovery room to assess for any undetected intra-operative complications (fracture or gross component malposition). These are not the x-rays used for formal assessment of component position – these are done at the 6 month office follow up visit.

Hospital care:

Patient in-hospital care and rehabilitation is standardized using our group's total knee replacement care map. Deep venous prophylaxis consists of sequential compression devices for 24 hours with elastic stockings while in hospital and rivaroxaban for a minimum of 2 weeks post-surgery. Analgesia is obtained oral narcotics and acetaminophen with patient-controlled intravenous analgesia used when necessary.

Follow up:

All patients will follow our group's pre-existing routine follow-up schedule: a fracture clinic visit 2 weeks post-op for surgical staple removal and wound check, a 8 week office visit for clinical, radiological examination and completion of the clinical outcome questionnaires, a 6 month post-op office visit for clinical & radiographic examination and completion of the clinical outcome questionnaires, followed by yearly visits for clinical & radiographic examination and completion outcome questionnaires. For the purposes of this study, data will be gathered until subjects reach two years from surgery.

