The only change from our normal clinical follow-up will be at the 8 weeks follow-up radiological examination. A 3 foot standing AP x-ray of the leg will be substituted for the routine AP x-ray of the knee, and a 3 foot lateral x-ray of the leg will be substituted for the lateral knee x-ray. These modified views increase x-rays exposure minimally, while providing proper standardized films for assessment of limb alignment and component alignment {Hewitt, 2001 #206;Jeffery, 1991 #210}.

Special Sub-group follow up:

15 patients from each arm of the study (30 patients in total) will be asked to participate in a CT scan sub-group to assess component rotation. While standardized plain x-rays are good for assessing component alignment in the coronal and saggital planes, CT scans are required to assess component rotation relative to the long axes of the femur and tibia {Jazrawi, 2000 #209;Berger, 1998 #196}. To minimize time commitment from patients, a single CT scan will be undertaken during the hospital stay using a standardized technique {Berger, 1998 #196}. This CT scan is in addition to the plain x-rays as previously described. This sample size of 30 patients was chosen based upon previously published work {Berger, 1998 #196}.

Data storage

Data for this study will be stored in the Concordia Joint Replacement Group's PHIA compliant database (HREB approval H2003:004). Data will be exported to SAS statistical analysis software in a de-identified fashion for statistical analysis.

Outcome Measures

Primary outcome measures:

1. Leg alignment
 - a. Frontal limb alignment as measured on the 3 foot standing film (fig.1-A).

- b. Sagittal limb alignment as measured on the 3 foot lateral film (fig.1-D & E).
- 2. Femoral component position
 - a. Varus/valgus alignment relative to mechanical axis of femur as measured on the 3 foot AP film (fig.1-A).
 - b. Flexion/extension alignment relative to mechanical axis of femur as measured on the 3 foot lateral film (fig.1-D).
 - c. Rotation relative to epicondylar axis as measured by CT scan
- 3. Tibial component position
 - a. Varus/valgus alignment relative to mechanical axis of tibia as measured on the 3 foot AP film (fig.1-C).
 - b. Amount of posterior slope as measured on the 3 foot lateral film (fig.1-E).
 - c. Rotation relative to tibial tubercle as measured by CT scan

[figure not shown]

Figure 1 - Limb Alignment

Secondary outcome measures:

1. EuroQol score at 1 and 2 years
2. Oxford 12 score at 1 and 2 years

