3. Pain Catastrophizing Scale score at 1 and 2 years
4. Knee Replacement Expectations score at 1 and 2 years
5. Visual analogue scales (VAS) for pain and satisfaction at 1 and 2 years
6. UCLA Activity Level score at 1 and 2 years.

Miscellaneous measures:

1. Surgical and tourniquet time
2. Number of instrument pans used
3. Length of hospital stay
4. Peri-operative complications such as deep venous thrombosis, pulmonary emboli, wound complications and cardiac events.

Sample Size

This trial is powered to detect a difference in post-operative frontal limb alignment between the two groups. The CJRG have recently had a computer navigation study accepted for publication assessing alignment with the same protocol as outlined in the study. The standard deviation for frontal plane alignment in the traditional instrumentation group was 3.1 degrees. Previous studies have indicated increased risk of early revision with alignment more than 3 degrees from the mechanical axis {Ritter, 1994 #334}. Assuming $p=0.05$ and power of 95%, a sample size of 29 per arm is required. Allowing for 20% drop-out requires 35 subjects per arm total.

Study End Points

The study will end when all enrolled patients are followed out clinically and radiographically to two years. No interim analysis is planned, as this would adversely affect significance testing. The surgeons involved in this study follow their patients closely in the post-operative period; any unforeseen significant complications arising from using the patient-specific custom cutting blocks that cannot be resolved would prompt cessation of the trial. This process is facilitated by the Concordia Joint Replacement Group's weekly planning & post-operative x-ray review rounds.

Analysis

Data for this study will be stored in the Concordia Joint Replacement Group's PHIA compliant database (HREB approval H2003:004). Data will be exported to SAS statistical analysis software in a de-identified fashion for statistical analysis. The two groups will be compared to assess the adequacy of randomization, relevant data will be assessed for normalcy, and the appropriate parametric and non-parametric tests will be used for comparing means and proportions between the two groups. Multiple regression analysis will be used to look for other factors that may affect post operative limb alignment and component position.

Dissemination

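### Enrolling 35 per arm does not keep the required 29 after a 20% drop-out: it keeps 28

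*Combined protocol and SAP*

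**What the plan says.** The Sample Size section powers the trial on post-operative frontal limb alignment. It gives one variability figure: "The standard deviation for frontal plane alignment in the traditional instrumentation group was 3.1 degrees". It cites earlier work on "increased risk of early revision with alignment more than 3 degrees from the mechanical axis", then sets the error rates and the resulting number: "Assuming $p=0.05$ and power of 95" per cent, for which "a sample size of 29 per arm is required". The next sentence gives the enrolment target: "Allowing for 20% drop-out requires 35 subjects per arm total".

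No inflation formula is shown, and the 20% is not tied to a visit. The Budget section uses the same 35 as the number of custom cutting blocks needed. No other section gives a different drop-out rate or enrolment number.

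**The concern.** A drop-out rate is ordinarily a share of the patients enrolled. On that meaning, the enrolled number multiplied by 0.80 should come to at least the evaluable number required. Here it does not. The plan therefore claims a property for its sample size (29 evaluable per arm after a 20% loss) that the numbers do not deliver. At stake is the accuracy of the sample size justification, which any reader can test with one multiplication. Enrolment, analysis and conclusions would not change.

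**Working it through.** **Inputs stated in the Sample Size section:** 29 evaluable per arm, 20% drop-out, 35 enrolled per arm, SD 3.1 degrees, alpha 0.05, power 95%.

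**Inputs assumed:** a between-group difference in means of 3 degrees, and two-sided testing. The section mentions 3 degrees only as a distance from the mechanical axis linked to revision risk, and it does not state sidedness. These inputs are used because they reproduce 29. They affect only steps 1 and 4.

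**Step 1. Reproduce 29.**
- Normal approximation: n = 2 × (1.960 + 1.645)² × (3.1/3)² = 27.75, so 28.
- Two-sample t-test: n = 28.75, so 29, matching the plan. A one-sided t-test would give 24.

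**Step 2. Check the drop-out allowance, using only the plan's own figures.**
- Remaining after 20% loss from 35: 35 × 0.80 = 28, which is less than 29.
- Enrolment needed to keep 29: 29/(1 − 0.20) = 36.25, so 37 per arm (74 in total, against 70).
- 36 × 0.80 = 28.8 is still short; 37 × 0.80 = 29.6 is enough.
- Loss that 35 can absorb: 35 − 29 = 6, and 6/35 = 17.1%. A 20% loss is 7/35.

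35 × 0.80 is exactly 28, so rounding does not explain the gap.

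**Step 3. Where 35 may have come from.** Two routes lead to it, and both are inferred:
- 29 × 1.2 = 34.8, rounded up to 35 (20% added to the evaluable number).
- 28/0.80 = 35 (correct inflation of the normal-approximation figure of 28).

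**Step 4. What one patient per arm costs, under the assumed inputs.**

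| Evaluable per arm | Power, t-test | Power, normal approximation | Difference detectable with 95% power (t-test) |
|---|---|---|---|
| 28 | 94.47% | 95.16% | 3.04 degrees |
| 29 | 95.17% | 95.77% | 2.99 degrees |

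The loss is about 0.7 percentage points of power.

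**The case against.** The best defence is that the section does not state the base of the 20%. If it is a margin added to the required number, 29 × 1.2 = 34.8 rounds up to 35 and the sentence agrees with itself. This probably explains the figure, but it is not the usual meaning of drop-out, and 35 enrolled still leaves 28 if a fifth of them are lost. The other route, 28/0.80 = 35, does not help either: the plan states 29, so one of its two numbers would still need correcting.

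A second defence is that the shortfall may never arise for the powered outcome. The section on follow-up says that "The only change from our normal clinical follow-up will be at the 8 weeks follow-up radiological examination", where the 3-foot films are taken, and Table 1 also puts leg alignment at 8 weeks. The Surgery section instead places the formal assessment of component position at 6 months. Either is well before the end of follow-up, since "data will be gathered until subjects reach two years from surgery". Loss by the time of the alignment films could be below 17%, leaving 29 or more. That is possible, but the plan gives no visit-specific rate to show it. It limits the consequence without making the sentence correct.

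Third, the effect is immaterial: one patient per arm, less than one point of power, and under the normal approximation 28 still meets 95%. This stands, and it is why the point is minor. It is also fair that the correction itself needs no power figure, because any such figure rests on inputs the plan does not state.

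**Conclusion.** The concern holds, as a minor arithmetic error. On the ordinary meaning of drop-out, 35 per arm leaves 28 after a 20% loss, not 29; it protects 29 only up to a 17.1% loss. That conclusion uses nothing beyond the plan's own 29, 20% and 35. The estimated cost, power of 94.5% instead of 95.2%, also depends on a 3-degree difference in means, SD 3.1 degrees in both arms and a two-sided t-test at 0.05. The trial is not materially underpowered on this account.

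**What to change.** Keep 35 per arm and replace the drop-out sentence in the Sample Size section with wording such as:

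> 35 per arm retains the required 29 evaluable with up to 17% drop-out (6 of 35); with 20% drop-out, 28 per arm remain.

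If the authors confirm the 3-degree between-group difference, the SD of 3.1 degrees and the two-sided t-test at 0.05, they can add that 28 per arm gives about 94.5% power. Otherwise the power clause should be left out.

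The cost is one sentence, with the stated allowance falling from 20% to 17%. Enrolment, block supply and analysis are untouched. The alternative, 37 per arm, would keep the 20% but add 4 patients in total (74 against 70) and would have to be reconciled with the 35 blocks in the Budget section, for under one point of power at a 20% loss. Restating the allowance is the more proportionate change.

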In an effort to address this problem, a variety of technologies have been developed to assist with positioning of the cutting blocks and balancing of knee ligaments. One of the newest technologies uses magnetic resonance imaging to create a three-dimentional computer model of the cartilage and bone of a disease knee. A 3-foot standing radiograph determines the mechanical alignment of the limb. The data from these two imaging modalities is combined to determine the ideal position for cutting both the tibia and the femur. The computer model and proposed cut locations are then forwarded in electronic file format for adjustment and approval by the treating surgeon. Because of the varying anatomy of each patient coupled with the unique nature of each patient's osteophyte pattern, patient-specific cutting blocks can then be rapidly manufactured. These cutting blocks sit on the patient's unique anatomical landmarks and position the bone cuts in the optimal locations based on the pre-operative imaging. The cutting blocks are held in place with traditional pins. In the case of an intra-operative discrepancy, the pins can be left in place with the cutting blocks removed and traditional instruments can be used to complete the procedure.

Custom-cutting blocks are touted to have several advantages over traditional instrumentation. With bone cuts being determined by pre-operative imaging, the alignment can be customized to the individual patients. Also, errors in alignment stemming from the intra- and extra-medullary alignment rods are removed. The preservation of the femoral and tibial canals may reduce blood loss in the perioperative period and reduce post-operative hemarthrosis and pain, thereby improving mobility and potentially leading to earlier discharge from hospital. One of the limitations of this new technology is additional cost. The cutting blocks themselves cost \$500 per patient. This is in addition to the cost of the MRI for pre-operative planning. While these costs are significant, if clinical outcome can be improved by either reduced length of stay or avoidance of mal-alignment by 3 degrees, then the cost would be mitigated immediately (in the case of length of stay) or in the long-term (based on reduced need for revision). While several companies currently are under taking similar studies with competitive products, each technique differs from the others and need to be assessed independently.

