- 3) Patients undergoing knee replacement revision surgery. These types of implants also have stems, making the use of image guided bone cuts inappropriate for the same reasons.
- 4) Patients scheduled for bilateral knee surgery (simultaneous or staged)

Procedure

Recruitment:

Potential participants will be identified by our group's research staff from the surgical booking list kept by the Concordia Replacement Group. Permission to review their medical chart for purposes of research and to contact them regarding participation in research will have been obtained using the group's database consent form (HREB approval H2003:004).

Research staff will contact potential participants by telephone approximately 3-5 months before their surgical date to explain the study and ask if they would like to participate. If they agree, they will be sent a cover letter, two copies of the study consent form, and copies of the clinical outcome scores to complete. They will be asked to sign the consent form (if no questions) and complete the questionnaires before meeting with study staff at the pre-anesthetic clinic, who will collate the forms and answer any further questions.

Randomization:

Randomization will occur after enrolment and subjects will be blinded to assignment group. All subjects will be scheduled for and receive the same MRI experience. It is not possible to blind the surgeon to the surgical technique. The block randomization process will be stratified by surgeon to ensure equal distribution between the two surgical techniques.

Surgery:

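### Surgeon (the stratification factor) and pre-operative questionnaire scores are not written into the treatment comparison: a valid analysis that gives up some precision, mainly on the questionnaires

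*Combined protocol and SAP*

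**What the plan says.** Under Procedure, Randomization: "The block randomization process will be stratified by surgeon to ensure equal distribution between the two surgical techniques". The Study design paragraph gives four surgeons. Block size is not stated.

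Under Procedure, Recruitment, patients are asked to "complete the questionnaires before meeting with study staff at the pre-anesthetic clinic". Table 1 also marks questionnaires and functional assessment as collected pre-operatively. The secondary outcome list gives each instrument as a score at 1 and 2 years and mentions neither change from baseline nor baseline adjustment.

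The Analysis section plans a check of group comparability and of normality. After that, "the appropriate parametric and non-parametric tests will be used for comparing means and proportions between the two groups". No covariate or stratum is named. It then adds: "Multiple regression analysis will be used to look for other factors that may affect post operative limb alignment and component position". No covariates are listed for that model, its treatment term is not mentioned, and questionnaire outcomes are outside its stated scope.

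**The concern.** When allocation is balanced within surgeon, part of the outcome variance that lies between surgeons cannot contribute to the difference between arms. A two-sample test still counts that variance in its standard error. The standard error is then too large on average, and the test rejects less often than its nominal level. In the same way, a pre-operative score that predicts the later score explains variance that an unadjusted comparison leaves in the error term.

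Efficiency is at stake, and it matters most for the questionnaires. They carry the secondary objective on knee function, the sample size was not set for them, and no adjusted analysis is planned. For alignment and component position the gap is smaller: a regression exists, but its content and its role in estimating the treatment effect are left open. Leaving both open also lets covariates be chosen after the data are seen.

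**Working it through.** **Inputs from the plan.** Four surgeons; stratified blocks; 35 per arm enrolled; 20% drop-out; significance level 0.05 (two-sided assumed). For the SD, the Sample Size section says: "The standard deviation for frontal plane alignment in the traditional instrumentation group was 3.1 degrees". The target difference is not stated outright. Three degrees is inferred from the malalignment threshold cited there.

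**Inputs assumed, because the documents do not give them.** Surgeon share of variance (ICC) 0 to 0.2; pre/post correlation r of 0 to 0.5; surgeon volumes equal (18/18/17/17) or unequal (28/20/14/8); blocks of 4 (2 and 6 also tried for the cost figures); drop-out at random.

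**Step 1: the plan's own figure.** With a standardised difference of 3/3.1 = 0.968 and a two-sided t-test, noncentral-t power is 95.2% at 29 per arm, so the stated 29 reproduces. With 35 x 0.8 = 28 per arm retained, power is 94.5%. The sample size therefore already rests on an unadjusted comparison.

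**Step 2: frontal alignment at 3 degrees.** Simulation with 20,000 replicates per cell, 70 enrolled, 56 retained, total SD held at 3.1:

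| ICC | Unadjusted, equal / unequal volumes (%) | Treatment + surgeon, equal / unequal (%) |
|---|---|---|
| 0 | 94.4 / 94.6 | 94.0 / 94.2 |
| 0.05 | 94.8 / 94.7 | 95.1 / 94.7 |
| 0.1 | 95.4 / 95.4 | 96.0 / 96.1 |
| 0.2 | 96.3 / 96.2 | 97.6 / 97.7 |

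Type I error of the test that ignores surgeon (equal / unequal volumes) is 5.2/4.9, 4.7/4.7, 4.5/4.3 and 3.6/3.8% at these four ICCs. A different set-up (64 patients, 16 per surgeon, fixed surgeon effects, no drop-out) gives 3.8% and 2.8% at surgeon shares of 0.1 and 0.2. The direction is the same, but the size depends on the set-up, so neither set of values is a property of this trial.

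**Step 3: questionnaires.** With 28 per arm, an unadjusted t-test has 80% power at 0.762 SD. At that difference, with equal volumes:

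| ICC | r | Unadjusted (%) | Treatment + surgeon + baseline (%) |
|---|---|---|---|
| 0 | 0 | 79.6 | 78.2 |
| 0 | 0.3 | 79.6 | 81.7 |
| 0 | 0.5 | 79.5 | 88.3 |
| 0.1 | 0 | 81.4 | 82.4 |
| 0.1 | 0.3 | 81.4 | 85.6 |
| 0.1 | 0.5 | 81.6 | 91.6 |

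**Step 4: patient equivalents at ICC 0.** Noncentral-t power of an unadjusted trial at 0.762 SD is 81.4% with 29 per arm and 88.2% with 35. The simulated 81.7% (r = 0.3) and 88.3% (r = 0.5) therefore correspond to about 29 and 35 per arm.

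**Step 5: cost if neither covariate predicts the outcome (ICC 0, r = 0).** Noncentral t given each allocation, over 1,200 allocations, block sizes 2, 4 and 6 and both volume patterns:
- Surgeon model: 0.30-0.41 point lost at 3 degrees, 0.62-0.86 at 2 degrees.
- Surgeon plus baseline: 1.36-1.68 points lost at 0.762 SD.

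**Step 6: CT subgroup.** With 15 per arm, surgeons falling at random and a difference of 1.0 SD (8,000 replicates), power without and with surgeon is 76.1/71.0% at ICC 0, 76.4/74.7% at 0.1 and 77.4/78.8% at 0.2. Adjustment can cost more than it returns here.

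**The case against.** The strongest reply is that nothing is wrong. The simple comparison is valid, errs on the safe side, and leaves the one powered outcome secure. Factors other than treatment could naturally include surgeon, and a reference to appropriate tests does not exclude stratified ones. Much of this stands. For alignment and component position the fault is loose wording, and the clear omission is confined to the questionnaires.

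It is also fair that the gain rests on assumed values whose range includes a small loss. The shared surgical technique, common care map and weekly joint x-ray review mean that a large surgeon effect cannot be presumed. The calculations cover linear models and t-tests only, so they do not settle the analysis of proportions or of strongly skewed, bounded scores. That is a reason to keep a rank-based test alongside the model.

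Two larger claims are tempting, and the evidence does not support either.
- **A bigger sample equivalent.** The shortcut 28/(1 - r²) gives 30.8 and 37.3 per arm at r = 0.3 and 0.5. It treats baseline as the only covariate and charges nothing for lost degrees of freedom or chance imbalance. The model with surgeon is worth about 29 and 35.
- **Pre-operative alignment as a further covariate.** Table 1 records leg alignment pre-operatively, and the background says of planning that "A 3-foot standing radiograph determines the mechanical alignment of the limb". But surgery aims to correct that alignment, so its correlation with the result may be near zero. At r = 0 with equal volumes, adding it to surgeon gives 93.5, 94.6, 95.7 and 97.4% at the four ICCs, below the 94.0, 95.1, 96.0 and 97.6% for surgeon alone. For sagittal alignment it is also unclear that a comparable pre-operative film exists: the statement that "a 3 foot lateral x-ray of the leg will be substituted for the lateral knee x-ray" concerns the 8-week visit only.

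**Conclusion.** The point holds as an optional gain in efficiency and a gap in prespecification. The plan stratifies by surgeon and collects pre-operative questionnaire scores, but does not say that either enters the treatment comparison.

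A reader might infer that ignoring the stratification invalidates the test, raises the false-positive risk or undermines the sample size. The documents support none of these. The error is conservative if there is a surgeon effect, and the 29 per arm was derived for an unadjusted comparison.

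The benefit falls mainly on the questionnaires. At 0.76 SD with no surgeon effect it is about 2 points of power at r = 0.3 and about 9 points at r = 0.5. It is larger if surgeons differ. ICC, r, surgeon volumes, block size and random drop-out are all assumptions, so these figures are illustrations over a range.

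**What to change.** Change the wording of the Analysis section as follows:
- For continuous plain-film alignment and component-position outcomes, take the treatment effect, with its 95% confidence interval, from a linear model with treatment and surgeon. Do not require pre-operative alignment.
- For each questionnaire with a pre-operative score, use treatment, surgeon and the pre-operative score of the same instrument.
- Keep the unadjusted or rank-based test as a sensitivity analysis.
- Keep simple comparisons for CT rotation (the plan says "15 patients from each arm of the study (30 patients in total) will be asked to participate in a CT scan sub-group"), for proportions such as alignment beyond 3 degrees, and for sparse complications.
- State that the regression on other factors is exploratory and does not supply the treatment effect.

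No new data or patients are needed. The price if surgeon and baseline turn out uninformative is about 0.3-0.4 point of power for the surgeon model at 3 degrees (0.6-0.9 at 2 degrees) and about 1.4-1.7 points for the questionnaire model at 0.76 SD.
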